6.1.1 Derived and Computed Variables

Demographics

Body Mass Index (BMI, kg/m²) will be calculated using the following formula:

$$BMI = Weight (kg) / Height^2 (m^2)$$

Immunogenicity

Values below the lower limit of quantification (recorded as "< LQ") will be set to half that limit (LQ/2).

Values above the initial upper limit of quantification (recorded as ">UQ") will be set to that upper limit (UQ). Samples which initially report ">UQ" will be further manually diluted and tested. These manually diluted and tested sample values will be reported in the listings only.

Titer greater or equal to a given threshold is defined as binary variable for non-missing values as:

- = 1, if the titer is superior or equal to the given threshold
- = 0, otherwise

Seroprotection is defined as binary variable for non-missing values as:

- = 1, if anti-HBs levels \geq 10mIU/mL in serum
- = 0, otherwise

Seroprotection rate (SPR) is the percentage (%) of subjects achieving seroprotection.

Statistical Analysis Plan

An initial result of >= 5.0 and <12.0 mIU/mL ("Indeterminate") required duplicate retest per Laboratory Procedure Manual. In the statistical analysis, if the anti-HBs serology result is initially indeterminate, then the average of initial and repeat results will be calculated. Seroprotection will be determined as follows: if the average of initial and repeat results is \geq 10 mIU/mL, then it will be considered seroprotected. If it is less than 10 mIU/mL, then it will be considered not seroprotected.

Geometric Mean Concentration

The GMC will be calculated using the following formula:

$$10^{\left\{\sum_{i=1}^{n}\log_{10}\left(t_{i}\right)\atop n\right\}}$$

where t_1, t_2, K , t_n are n observed immunogenicity titers/concentrations.

Solicited Adverse Events

Reactions at the site of injection (redness/erythema, pain, tenderness, swelling/edema, pruritus), systemic reactions (nausea/vomiting, diarrhea, headache, fatigue, myalgia) and vital signs abnormalities (fever, tachycardia, bradycardia, hypertensions, hypotension, changes in respiratory rate).

Unsolicited Adverse Events

All adverse events will be characterized according to the date of occurrence related to the vaccination phase as follows:

- Emergence before vaccination phase: start date before the first date of injection of study vaccine.

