- **Emergence during vaccination phase**: start date on or after the first date of injection of study vaccine or, adverse event increase in severity including to "serious" adverse event.

If an adverse event start date is equal to the first date of vaccination injection, missing or unknown, the adverse event will be considered as emergent.

When start and/or end dates of an adverse event are only partially known, adverse events will be categorized as emergent before, during (or after) vaccination phase using the following rules:

• If the partial end date is before (<) the first study vaccination (i.e., year or year & month is/are before the first study vaccination year or year & month) then the adverse event is emergent before vaccination phase.

Statistical Analysis Plan

If the partial start date is equal or after (≥) the first study vaccination (i.e., year or year & month is/are after or the same as the first study injection year or year & month) then the adverse event is emergent during vaccination phase.

The **maximum event severity** is the greatest severity associated with a preferred term for a reported adverse event according to the following order: Mild < Moderate < Severe < Potentially life threatening. Unknown/ Missing severity is considered as potentially life threatening.

Multiple AEs with the same PT for the same subject are counted only once.

Vaccination-related Adverse Events are those for which the cause has been evaluated by the investigator, and recorded either as very likely/certain, possibly related, probably related or unknown/missing.

Pre-Study, Concomitant and Post-Study Medications

A **pre-study medication** is a medication used only before the first study vaccination (i.e. medication end date < first study vaccination date).

A **post-study medication** is a medication used only after study termination (i.e. medication start date > study termination date). This will not be collected in the clinical database and will not be reported in the CSR.

All other medications are **concomitant**.

When start and/or end dates of a medication intake are missing, the medication is considered as concomitant with the study vaccination schedule.

If the first study vaccination date is missing then the medication is considered as concomitant with the study vaccination schedule, provided that the study vaccine was administered to the subject.

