6.3.14.3 Unsolicited Adverse Events

Treatment-emergent adverse events (TEAEs) are defined as those adverse events that either start or worsen on or after the date of first vaccination.

All following TEAEs will be included in the summary tables:

• All AEs occurred on the day of vaccination (vaccination 1, vaccination 2 or vaccination 3) and during the next 27 days [date of vaccination + 27 days]

AND

^{**} Oral temperature; no recent hot or cold beverages or smoking.

^{***} When resting heart rate is between 60 - 100 beats per minute. Use clinical judgement when characterizing bradycardia among some healthy subject populations, for example, conditioned athletes.

Statistical Analysis Plan

• SAEs, medically significant events (i.e., AEs medically attended) or new onset of chronic illnesses through the date of end study

If a subject missed one or two vaccination injections, the AEs for the corresponding vaccination injections will not be included in the summary. For example, one subject missed vaccination 2, the AEs for the day of vaccination 2 and during the next 27 days will be missing and not be included in the summary tables and figures.

Solicited adverse events continuing beyond Day 7 will be coded by MedDRA and combined with the respective unsolicited adverse events.

For AEs included in the summary tables defined above, numbers of AEs will be summarized by System Organ Class (SOC) and Preferred Term, and also by severity/causality to vaccine. The summaries will be presented by vaccination (any vaccination, vaccination 1, vaccination 2 and vaccination 3) and interval of onset as follow:

- Day 1 to Day 28
 where the AEs will include AEs occurred on/after Day 1 (date of vaccination) until earliest date of (Day 28, date of next vaccination-1, end of study)
- Day 29 to end of considered interval
 where the AEs will include SAEs, medically significant events (i.e., AEs medically
 attended) or new onset of chronic illnesses occurred on/after Day 29 to earliest date of
 (date of next vaccination-1, end of study)
- Day 1 to end of considered interval where the AEs will include AEs occurred on/after Day 1 (date of vaccination) until earliest date of (date of next vaccination-1, end of study)

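### SAP 6.1.1 gives no precedence to a known end date before the first vaccination, so its missing-date rules contradict its own definitions of pre-study medication and treatment-emergent AE

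*SAP*

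**What the plan says.** **Medications (SAP 6.1.1).** A pre-study medication "is a medication used only before the first study vaccination (i.e. medication end date < first study vaccination date"). The start date plays no part in this definition. A post-study medication is one begun only after study termination, and these are not collected. Everything else is concomitant. The missing-date sentence follows: "When start and/or end dates of a medication intake are missing, the medication is considered as concomitant with the study vaccination schedule".

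**Adverse events (SAP 6.1.1).** An event belongs to the period before the vaccination phase if it has a "start date before the first date of injection of study vaccine". If the AE "start date is equal to the first date of vaccination injection, missing or unknown, the adverse event will be considered as emergent". Two rules then deal with partial dates:

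- The first begins "If the partial end date is before (<) the first study vaccination". It assigns the event to the period before vaccination when the year, or the year and month, of the end date is earlier than that of dose 1.
- The second makes an event emergent when the year, or the year and month, of its partial start is the same as or later than that of dose 1.

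**Treatment-emergent AEs (SAP 6.3.14.3).** These are "those adverse events that either start or worsen on or after the date of first vaccination".

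Neither set of rules is given an order of precedence.

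**The concern.** Treating an unknown date as emergent or concomitant is a sound worst-case convention when timing is uncertain. It is not needed when the record carries an end date before dose 1, because that date settles the question: the event or drug was over. The SAP's default still applies to such records, and the result disagrees with the SAP's own definitions.

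Such records are possible. Protocol 7.2 has AEs documented from written consent. Screening may take place up to 28 days before Visit 1 (Protocol 6.3.1), and the schedule of events collects both unsolicited AEs and medications at screening. SAP 6.3.14.3 plans a listing of pre-vaccination AEs alongside treatment-emergent ones, so the before/after split is used in reporting.

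At stake are the correct labelling of individual records in the AE listings and tables and in the Safety Set concomitant-medication summary (SAP 6.3.11), and a specification that two programmers would code in the same way.

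**Working it through.** The plan gives no figure to reproduce on this point. The check is to apply the SAP 6.1.1 rules literally to combinations of start and end date. The only added input is an illustrative first vaccination date of 20 March 2018, which is an assumption used to exercise the rules.

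| # | Record | Start | End | What the rules give |
|---|---|---|---|---|
| 1 | AE | missing | 10 Mar 2018 | Missing-start rule: emergent. No other date rule applies. |
| 2 | AE | Mar 2018, or 2018 | 10 Mar 2018 | Partial-start rule: emergent. The complete end date is not used. |
| 3 | AE | missing | Feb 2018 | Missing-start rule: emergent. Partial-end rule: before. Conflict. |
| 4 | AE | 2018 | Feb 2018 | Partial-start rule: emergent. Partial-end rule: before. Conflict. |
| 5 | Medication | missing | 10 Mar 2018 | Definition: pre-study. Missing-date sentence: concomitant. Conflict. |
| 6 | Medication | partial | 10 Mar 2018 | Definition: pre-study. No conflict. |
| 7 | AE or medication | missing | missing | Emergent or concomitant. A reasonable default. |

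**Cases 1 and 2.** The event ended 20 − 10 = 10 days before dose 1. Its start cannot be later than its end, so it started before dose 1, and it could not worsen afterwards. It fails the definition of a treatment-emergent AE, yet the rules call it emergent.

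**Cases 3 and 4.** Here the end-date rule does apply and gives the right answer, but a second rule gives the opposite one. Set beside cases 1 and 2, the pattern is odd: a vague end date (February) can bring a record back to the pre-vaccination period, while an exact one (10 March) cannot.

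**Case 5.** Consider what the missing-start clause adds when the end date is known.

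- If the end date is on or after dose 1, the drug is not pre-study, and the residual category already makes it concomitant. The clause changes nothing.
- If the end date is before dose 1, the definition says pre-study and the clause says concomitant.

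So, when the end date is known, the clause changes the class only of drugs known to have stopped before dose 1.

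**With a known earlier end date checked first.** Cases 1 to 4 become before vaccination and case 5 becomes pre-study. Cases 6 and 7 are unchanged, so the worst-case default survives where it is needed.

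**The case against.** **The SAP does not ignore end dates.** This is correct. A reader might infer that the rules look only at the start date. The text does not support that: pre-study medication is defined by the end date, the medication missing-date sentence is triggered by a missing start or a missing end, and the AE rules use a partial end date in an earlier month or year. The gap is narrower: a complete end date for AEs, and precedence for both sets of rules.

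**A programmer may apply the definition first.** For medications, this would give the right class. A reader might infer that every such medication is misclassified. The documents show a contradiction with no stated order, and the outcome depends on how it is coded.

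**Other conditions guard the AE tables.** SAP 6.3.14.3 limits the main tables to events on the day of a vaccination or in the next 27 days, plus serious, medically attended and new chronic events through study end. Its interval tables require occurrence on or after Day 1, and its additional tables require occurrence from the first vaccination onward. The SAP does not say how an event with a missing start is placed in these windows. Entry of a pre-vaccination event into those tables is therefore possible but not established.

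**Such records are unusual.** The start date is among the items recorded for each AE (Protocol 7.2.1), and the eCRF system has checks for incomplete data (Protocol 10.2). Signs and symptoms present before the first injection go to medical history (Protocol 6.1.4), and pre-existing conditions are not AEs unless they worsen (Protocol 7.1.3). This limits the number of records but does not resolve the conflicting rules.

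**A conservative default is harmless.** This holds for ambiguous dates. A record known to have ended before dose 1 is not ambiguous.

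**Conclusion.** The point holds as a minor specification error. For AEs with a missing start, or a partial start in the same month or year as dose 1, and a complete end date before dose 1, the rules give a class that the SAP's own definition excludes. For AEs with a partial end date in an earlier month or year, and for medications with a missing start and a known earlier stop date, the rules can give two opposite answers with no stated order.

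The effect is confined to descriptive outputs. Protocol 9.8 attaches no hypotheses to safety, the rules are identical in both arms, and the co-primary and secondary seroprotection analyses do not use these flags. The number of affected records cannot be derived, because the documents do not say how often a start date is missing while an end date is known. That it is probably small is a judgement based on the collection procedures cited above.

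A reader might also infer that restricted products stopped before dose 1 would count as on-study use and so affect the per-protocol set. The documents do not support this. Under SAP 6.2.5 and 6.3.7.2, exclusion for a prohibited medication rests on its judged impact and timing, assessed before unblinding, and is not tied to the concomitant flag.

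**What to change.** Add one rule to SAP 6.1.1, ahead of both sets of date rules: *an AE or medication whose end date (complete, or partial but unambiguous) is before the first vaccination is pre-vaccination or pre-study, whatever its start date.* State that the worst-case rules apply only when the end date is missing, ongoing, ambiguous, or on or after the first vaccination.

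The cost is one sentence in the SAP and one condition in each derivation. Records with truly uncertain timing keep their present classification, and no inferential result changes. The SAP's introduction allows amendment before database lock. After lock, the same rule could be applied and described in the clinical study report as a deviation.

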6.2 Analysis Sets

6.2.1 All Enrolled Set

The all enrolled set will be defined as all screened subjects who provide informed consent and provide demographic and/or baseline screening assessments, regardless of the subject's randomization and treatment status in the study.

6.2.2 Safety Set

All subjects in the All Enrolled Set who receive a study vaccination. Subjects will be analyzed as vaccinated, i.e., a subject will be assigned according to the vaccination received.

Statistical Analysis Plan

In case of vaccination error, subjects will be analyzed as "treated" (i.e., according to the vaccine a subject receives, rather than the vaccine to which the subject is randomized).

6.2.3 Intent-to-Treat (ITT)

All subjects in the All Enrolled Set who were randomized.

In case of vaccination error, subjects in the ITT will be analyzed "as randomized" (i.e., according to the vaccine a subject was designated to receive, which may be different from the vaccine the subject actually received). Any subject who received the wrong vaccination will not be excluded from the ITT.

6.2.4 Full Analysis Set (FAS)

All subjects in the All Enrolled Set who receive at least one vaccination and provide at least one evaluable serum immunogenicity sample both at baseline and after baseline.

In case of vaccination error, subjects in the FAS will be analyzed "as randomized" (i.e., according to the vaccine a subject was designated to receive, which may be different from the vaccine the subject actually received). Any subject who received the wrong vaccination will not be excluded from the FAS.

If a subject is unblinded during the study, he/she will be included in the FAS.

6.2.5 Per Protocol Set (PPS)

All subjects in the FAS who:

- received all 3 vaccinations
- have an evaluable serum immunogenicity samples at baseline and at the time point of interest
- are sero-negative at baseline
- had no major protocol deviations leading to exclusion, which will be identified prior to unblinding.

A major protocol deviation for the purpose of exclusion from the PPS is defined as a protocol deviation that is considered to have a significant impact on the immunogenicity result of the subject. These will be identified prior to unblinding and analysis and may include:

- subjects enrolled who did not meet study entry criteria
- subjects who did not receive the correct treatment
- subjects who attended study visits outside of the following windows:
 - o V2/Day 28 (- 7 / +14 days)
 - o V3/Day 56 (-7/+14 days)
 - o V4/Day 168 (+/-28 days)
 - o V5/Day 196 (-7 / +14 days)

Statistical Analysis Plan

- subjects who developed withdrawal criteria but were not withdrawn
- subjects who received a prohibited concomitant medication [as per exclusion criteria], if the
 medication and the timing of its administration is considered to have a significant impact on the
 reliability of subject immunogenicity result
- subjects with a deviation identified through monitoring visits or otherwise, where the deviation is judged to impact the reliability of subject immunogenicity results

In case of vaccination error, subjects in the PPS will be analyzed "as randomized" and the subject who received the wrong vaccination will be excluded from the PPS. If a subject receives a vaccine from the wrong kit number, but the same as the one the subject was randomized to, the subject will not be removed from the PPS.

If a subject is unblinded during the study, except for suspected unexpected serious adverse reaction (SUSAR), he/she may be excluded from the PPS based on sponsor's decision with respect to any potential bias that may be introduced in the analysis of the primary and key secondary immunogenicity analyses.

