1.2 Immunogenicity of licensed vaccines

Monovalent HBV vaccines, such as Engerix-B®, licensed in Canada, European Union (E.U), and the United States (U.S.) are second-generation vaccines using recombinant DNA technology to express the HBV DNA sequence coding for the small hepatitis B surface antigen (HBsAg) in yeasts. The 1 mL dose of Engerix-B® containing 20 µg of HBsAg is the form approved for the immunization of healthy adults. In adults, the most commonly recommended immunization schedule consists of three injections of vaccine: two injections 4 weeks apart, followed by a third injection 24 weeks after the initial injection.

A serum concentration of hepatitis B surface antigen antibody (anti-HBs) \geq 10 mIU/mL after vaccination is considered protective⁴, and is associated with long term immunity to hepatitis B⁵. Therefore, the seroprotection rate (SPR), i.e., the percentage of subjects achieving a serum concentration of hepatitis B surface antigen antibody (anti-HBs) \geq 10 mIU/mL after vaccination, is widely used as a surrogate endpoint for evaluating anti HBV vaccines.

While the SPRs elicited by currently licensed hepatitis B vaccines in children and adolescents are high (≥98%)⁶, up to 10% of all adults fail to achieve anti-HBs levels ≥10 mIU/mL after a three-dose schedule⁶, and are considered non-responders to hepatitis B vaccination. The proportion of adult non-responders is even higher in individuals age 30 years and above, where there is a well-documented age-dependent decline in response rate to currently licensed HBV vaccines^{7,8}. In recent phase 3 trials where Engerix-B® was the comparator, SPRs 4 weeks after completion of the three-dose regimen were 74%, 72% and 68%, in adults 40-49, 50-59 and 60-69 years old, respectively⁸⁻¹⁰. In addition to age and genetic factors, other factors are known are known to be associated with reduced immunogenicity of HBV, including obesity¹¹, and, as recently reviewed by Yang Tian et al in 2016, male gender, smoking, diabetes, and concomitant disease¹².

Moreover, compliance with the primary three-dose schedule is low, with up to 40% of vaccinees missing the third injection, resulting in inadequate clinical protection against HBV infection¹³.

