9.6 Secondary Immunogenicity Objectives

9.6.1 Secondary Immunogenicity Hypotheses

If the co-primary hypotheses are significant, the following secondary hypotheses will be tested in the following pre-specified order, with each hypothesis using a two-sided 5% significance level.

1) Non-Inferiority of Sci-B-Vac[™], 20 weeks following the second vaccination, compared to Engerix-B®, 4 weeks following the third vaccination, will be assessed using the PPS3 analysis set for the entire study population (i.e., adults ≥ 18 years old). The non-inferiority margin is set at 5%. The null and alternative hypotheses are as follows;

Null Hypothesis: SPR(Sci-B-Vac[™]) –SPR(Engerix-B[®]) <= -5%

Alternative Hypothesis: SPR(Sci-B-Vac[™]) –SPR(Engerix-B[®]) > -5%

Non-inferiority will be assessed using the lower bound of the two-sided 95% confidence interval. If the lower bound is greater than -5%, Sci-B-Vac[™]20 weeks following the second vaccination will be declared non-inferior to Engerix-B[®] 4 weeks following the third vaccination, and the next secondary hypothesis will be tested.

2) Non-Inferiority of Sci-B-Vac[™] 4 weeks following the second vaccination compared to Engerix-B[®] 4 weeks following the third vaccination will be assessed using the PPS for the entire study population (i.e., adults ≥ 18 years old). The non-inferiority margin is set at 5%. The null and alternative hypotheses are as follows;

Null Hypothesis: SPR(Sci-B-Vac[™]) –SPR(Engerix-B[®]) <= -5%

Alternative Hypothesis: SPR(Sci-B-Vac[™]) –SPR(Engerix-B[®]) > -5%

Non-inferiority will be assessed using the lower bound of the two-sided 95% confidence interval. If the lower bound is greater than -5%, Sci-B-Vac™ 4 weeks following the second vaccination will be declared non-inferior to Engerix-B® 4 weeks following the third vaccination.

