9.6.2 Statistical Methods for Secondary Immunogenicity Analyses

The secondary endpoints of SPR 4 weeks following the second vaccination with Sci-B-Vac[™] and 20 weeks following the second vaccination Sci-B-Vac[™], each compared with SPR 4 weeks following the third vaccination with Engerix-B[®] will be analyzed using data from all centers will be pooled together. The difference in adjusted proportions and two-sided 95% Cis, calculated using the Miettnen and Nurminen method, will be reported. will be calculated based on these models. For immunogenicity data, it may be reasonable to consider missing immunogenicity values as missing completely at random (MCAR), i.e., not informative. Therefore, the analysis will comprise a complete case analysis only without introducing any bias. Imputation methods will not be used. These analyses will be conducted using the PPS.

The impact of center will be investigated through funnel plots.

Sensitivity analyses using the same modeling approach outlined above will be conducted using the FAS, for both secondary analyses. These analyses will be reported both with and without patients in the FAS who are seropositive at baseline. Additional sensitivity analyses will be conducted using a Log Linear model, to adjust for age group. Factors for treatment and age group will be included in the model.

Analyses of the above secondary endpoints will also be conducted and reported by key sub-groups using the sub-groups identified in Section 9.3.7.

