6.3.13.3 Statistical Methods for Secondary Objective Analyses

If the co-primary hypotheses are significant, the following secondary hypotheses will be tested in the following pre-specified order, with each hypothesis using a two-sided 5% significance level. If an endpoint fails to reach statistical significance, following hypothesis tests will not be performed.

1) Non-Inferiority of Sci-B-VacTM, 20 weeks following the second vaccination, compared to Engerix-B®, 4 weeks following the third vaccination, will be assessed using the PPS for the entire study population (i.e., adults \geq 18 years old). The non-inferiority margin is set at 5%. The null and alternative hypotheses are as follows;

Null Hypothesis: SPR(Sci-B-VacTM) –SPR(Engerix-B®) <= -5%

Alternative Hypothesis: SPR(Sci-B-VacTM) –SPR(Engerix-B®) > -5%

Statistical Analysis Plan

Non-inferiority will be assessed using the lower bound of the two-sided 95% confidence interval. If the lower bound is greater than -5%, Sci-B-VacTM 20 weeks following the second vaccination will be declared non-inferior to Engerix-B® 4 weeks following the third vaccination, and the next secondary

hypothesis will be tested.

2) Non-Inferiority of Sci-B-Vac[™] 4 weeks following the second vaccination compared to Engerix-B® 4 weeks following the third vaccination will be assessed using the PPS for the entire study population (i.e., adults ≥ 18 years old). The non-inferiority margin is set at 5%. The null and alternative hypotheses are as follows;

Null Hypothesis: SPR(Sci-B-VacTM) –SPR(Engerix-B®) <= -5%

Alternative Hypothesis: SPR(Sci-B-VacTM) –SPR(Engerix-B®) > -5%

Non-inferiority will be assessed using the lower bound of the two-sided 95% confidence interval. If the lower bound is greater than -5%, Sci-B-VacTM 4 weeks following the second vaccination will be declared non-inferior to Engerix-B® 4 weeks following the third vaccination.

The analysis for secondary endpoints will be conducted the same approach using the PPS for the non-inferiority co-primary analysis (Section 6.3.13.2). The estimated proportions and two-sided 95% CIs for Engerix-B® at Day 196 and Sci-B-VacTM at Day 56 or Sci-B-VacTM at Day 168 as well as the difference in proportions between Engerix-B® and Sci-B-VacTM [SPR(Sci-B-VacTM) – SPR(Engerix-B®)] and two-sided 95% Miettinen-Nurminen CIs will be calculated and reported. Funnel plot will be produced to investigate the impact of center.

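### The two-dose non-inferiority tests of Sci-B-Vac are decided on a per-protocol set that requires the third dose, which is given after the two-dose samples are drawn; this matters mainly at Day 56

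*SAP*

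**What the plan says.** SAP 6.2.5 and Protocol 9.3.5 each define a single PPS. Members must have "received all 3 vaccinations", and must "have an evaluable serum immunogenicity samples at baseline and at the time point of interest" (SAP wording). They must also be seronegative at baseline and free of major deviations leading to exclusion. Only the sample criterion follows the time point; the dose criterion does not.

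SAP 6.3.13.3 sets out two secondary hypotheses, tested in a fixed order after the co-primaries, "with each hypothesis using a two-sided 5% significance level". The first compares Sci-B-Vac at Day 168 with Engerix-B at Day 196: "4 weeks following the third vaccination, will be assessed using the PPS for the entire study population". The second compares Sci-B-Vac at Day 56 with the same comparator and names the same set. Protocol 9.6.2 agrees: "These analyses will be conducted using the PPS". Protocol 9.6.1, however, says that the Day 168 test "will be assessed using the PPS3 analysis set for the entire study population", and PPS3 is defined nowhere.

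FAS sensitivity analyses are planned for both tests (SAP 6.3.13.3, Protocol 9.6.2). The FAS requires at least one vaccination and does not require dose 3 (SAP 6.2.4).

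**The concern.** A per-protocol rule should restrict the analysis to subjects whose result reflects the regimen under test. For the Sci-B-Vac side of these tests the regimen is two doses. The Day 56 sample is taken 16 weeks before dose 3 is due, and the Day 168 sample is taken before dose 3 at the same visit. Dose 3 cannot affect either result. Requiring it adds nothing to the purity of a two-dose comparison and selects subjects on a later event.

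The plan itself provides for such subjects. Individual stopping rules end further vaccination (Protocol 7.8). Later doses may be withheld after a prohibited medication (Protocol 6.1.9). A subject withdrawn from the product may stay in immunogenicity follow-up (Protocol 4.3.2). Some of these reasons relate to health and could relate to immune response.

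At stake is a confirmatory claim that two doses of Sci-B-Vac are non-inferior to three of Engerix-B. The protocol's background supports interest in fewer injections by poor return for dose 3, "with up to 40% of vaccinees missing the third injection", so those who stop after two doses should not be excluded from the deciding analysis without a reason.

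**Working it through.** **1. The plan's own figures.** There are none to reproduce. Neither document gives a two-dose SPR, a power for the two-dose tests, a dropout allowance or an expected rate of missing dose 3. The 40% in Protocol 1.2 describes vaccinees in general, not this trial.

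**2. Whom the three-dose rule removes.** The useful count is not everyone who misses dose 3. It is those who miss dose 3 and would otherwise qualify, including having the sample at that time point.

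| Sci-B-Vac subject after two doses | Day 56 result | Day 168 result |
|---|---|---|
| Attends V4, bled, vaccinated | kept | kept |
| Attends V4, bled, not vaccinated | removed by the dose rule | removed by the dose rule |
| Does not attend V4, no dose 3 | removed by the dose rule | no sample, so excluded under any PPS |

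The third row is why the point matters mainly at Day 56. Day 168 is also tested first, so the Day 56 test is reached only if Day 168 passes.

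**3. Formula for the bias.** Let m be the share of otherwise eligible Sci-B-Vac subjects with two doses and a sample but no dose 3. Let g be their SPR deficit relative to those who go on to dose 3. Then

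SPR(all two-dose) = (1 − m) × SPR(completers) + m × [SPR(completers) − g] = SPR(completers) − m × g,

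so the PPS estimate exceeds the two-dose SPR by m × g. The bias is zero if g = 0, favours Sci-B-Vac if g > 0, and works against it if g < 0.

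**4. Illustration for Day 56 only.** Both m and g are assumptions. The other inputs are 782 per arm (Protocol Summary), an Engerix-B SPR of 0.81 (SAP 4) and the 5-point margin (SAP 6.3.13.3). The error column is the exact probability that the Miettinen-Nurminen lower limit exceeds −5% when the true two-dose SPR is 0.81 − 0.05 = 0.76. The Sci-B-Vac PPS rate is 0.76 + m × g, and each arm has 782 × (1 − m) subjects (743, 704 and 665).

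| m | Removed from 782 | g | Bias = m × g | One-sided error (nominal 2.5%) |
|---|---|---|---|---|
| 5% | 39 | 0 | 0 | 2.5% |
| 5% | 39 | 10 points | 0.5 points | 4.2% |
| 5% | 39 | 20 points | 1.0 points | 6.9% |
| 10% | 78 | 10 points | 1.0 points | 6.7% |
| 10% | 78 | 20 points | 2.0 points | 15.2% |
| 15% | 117 | 10 points | 1.5 points | 9.9% |
| 15% | 117 | 20 points | 3.0 points | 27.6% |

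At m = 2% the bias is 0.02 × 10 = 0.2 points or 0.02 × 20 = 0.4 points. If the Sci-B-Vac arm uses a set that does not require dose 3, the error stays at about 2.5% in every row. These values of m should not be carried over to Day 168, where m counts only the second row of the table in step 2.

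**The case against.** The strongest reply has four parts.

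*Every Sci-B-Vac subject sampled on schedule at Day 56 or Day 168 after both earlier doses gives a two-dose result, whether or not dose 3 follows.* This stands. A reader might infer that the PPS discards the very people the two-dose question is about. The documents do not support that: it discards only those who stop after two doses.

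*The direction of bias is assumed.* This also stands. The trial is double-blind and serology is withheld until database lock (Protocol 5.6.2), so receipt of dose 3 cannot depend directly on the antibody result. Selection could act only indirectly, through health, tolerability, medication or adherence. A reader might infer that the two-dose SPR is inflated, or that 40% non-return implies a large removed group. Neither follows, and at Day 168 non-attenders have no sample in any case.

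*The V4 and V5 windows in SAP 6.2.5 do not automatically strike out a Day 56 result.* Correct. They are listed as possible grounds, subject to a judgement of impact on the immunogenicity result before unblinding. The text permits such an exclusion without requiring it, and the wording should close that gap.

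*The FAS analyses already keep these subjects, and the present PPS treats both arms alike.* This stands in part. The FAS results are supportive and do not decide the test; the FAS can also include subjects with only one dose, so it is not a two-dose per-protocol set. The symmetry is formal: for Engerix-B, dose 3 precedes the Day 196 outcome and belongs to the regimen, while for Sci-B-Vac it follows the outcome.

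**Conclusion.** The point holds. The set that decides the two-dose tests conditions the Sci-B-Vac results on a later event, and nothing in either document relaxes the rule for Day 56 or Day 168. It should be corrected, chiefly for Day 56. At Day 168 the rule reaches only subjects who attend V4, are bled and are not vaccinated.

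The size and direction of any bias are unknown. It is m × g, and the documents give neither term. The 0.5 to 3.0 points illustrated for Day 56 rest wholly on an assumed 5–15% removed and a 10–20 point deficit. With no deficit there is no bias and the error rate is nominal. The documents therefore support a finding that the analysis set does not fit the question, not a finding that the tests are biased in favour of Sci-B-Vac. The co-primary non-inferiority test at Day 196 is unaffected, because there the three-dose rule matches the regimen.

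**What to change.** Before unblinding, define the PPS by time point in SAP 6.2.5 and Protocol 9.3.5:

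- **Sci-B-Vac, Day 56 and Day 168:** doses 1 and 2 received, seronegative at baseline, evaluable sample at that time point, and no major deviation up to that sample. A V4 or V5 window breach then cannot remove a Day 56 result.
- **Day 196:** keep the three-dose rule for the co-primary non-inferiority test and the Engerix-B comparator. State that Engerix-B subjects without dose 3 are excluded from that comparator.
- **Exploratory comparisons at Day 28, 56 and 168:** apply the same time-point rule to both arms.
- **Sensitivity analysis:** report both two-dose tests on the current all-completer PPS, alongside the planned FAS analyses.
- **Naming:** reconcile PPS3 in Protocol 9.6.1 with the PPS named in Protocol 9.6.2 and the SAP.

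The cost is wording, extra PPS flags and several PPS counts to report. One small downside should be stated: selection will differ between arms, with all two-dose Sci-B-Vac subjects set against Engerix-B completers. Each arm is then held to the regimen under test. If completers respond better, the difference works against Sci-B-Vac, which is conservative for non-inferiority. There is no loss of power from subject numbers. With both SPRs at 0.81 and no deficit, power is 70.2% with the time-point set against 68.9% with the current PPS at m = 5%, and 69.4% against 66.6% at m = 10%.
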